#### **A4c. Aim 3.**

**Study/Design Overview:** Aim 3 will focus on completing phase 2 of the eHealth intervention development, which will be a formative evaluation. For this portion of the study we will collect both qualitative and quantitative data from a new sample of patients using same inclusion/exclusion criteria in Table 2. This portion of the study will help to determine usability, acceptability, engagement with the intervention, and potential problems with completing the intervention and collecting data in a complete and rigorous manner.

Participant recruitment and sampling: Participant recruitment and sampling will follow steps described in Aim 2. The sample size selected for this aim (n=15) is in line with samples recommended for formative evaluations and pilots. The sample is attainable based on rationale presented in Aim 2. The analytical rationale for the sample size is based on the proposed analyses presented below.

Procedures: Veterans recruited for this aim will be asked to complete 1) baseline questionnaires to understand the clinical make-up of the sample and unobserved patient characteristics that may impact our formative evaluation findings, 2) the intervention, and 3) a semi structured interview to complete the formative evaluation.

Self-report measures: These quantitative measures will be used to better understand the makeup of our sample in terms of clinical characteristics and treatment readiness that may not otherwise be observable from the structured data in their EHRs: **Patient Health Questionnaire 9 (PHQ-9)**, 9-item instrument that assesses the symptoms of depression corresponding to the Diagnostic and Statistical Manual Version 5 (DSM-5) diagnostic criteria for a major depressive episode. Item responses are on a four-point scale (from occurring “not at all” to “nearly every day” over the past two weeks) resulting in a score range from 0 to 27. The PHQ-9 has similar psychometric properties to other measures of depression. PHQ-9 is favored for its brevity and ease of use in clinical settings (Cameron et al, 2011).

**Posttraumatic Stress Disorder Check List for DSM-5 (PCL-5)**, 20-item self-report of the severity of PTSD symptoms in the past month using a 5-point scale (0-4), ranging from “Not at all” to “Extremely.” A cut-point of 50 (range 0-80) represents a probable diagnosis of PTSD.

**Negative affect and distress:** The PANAS (Watson, Clark, & Tellegen, 1988), 20-item scale consisting of adjectives that describe mood states. Respondents will rate each mood adjective on a 0-4 scale (0 very slightly or not at all to 4 extremely). The questionnaire is divided into two subscales of positive affect and negative affect. The PANAS-N subscale will be used as a measure of subjective distress. The PANAS is widely used and has good reliability and validity (Mackinnon et al., 1999; Watson et al., 1988).

**Difficulties in Emotion Regulation Scale (DERS; Gratz & Roemer, 2004)**, 41-item, self-report measure developed to assess clinically relevant difficulties in emotion regulation: (a) awareness and understanding of emotions; (b) acceptance of emotions; (c) the ability to engage in goal-directed behavior, and refrain from impulsive behavior, when experiencing negative emotions; and (d) access to emotion regulation strategies perceived as effective. These characteristics are hypothesized to predict treatment initiation and may impact intervention uptake.

**Affective Control Scale (ACS; Williams et al., 1997)**, 42-item self-report instrument designed to assess anxiety about loss of control over a person's emotions and a person's reactions to those emotions (Williams et al., 1997). The scale is composed of four subscales measuring apprehension about the experience of different emotions: anger, positive emotion, depressed mood, and anxiety. These characteristics may impact intervention engagement.

**Pretreatment Self-Efficacy** (Yeager et al, 2018), 8-items that begin with the sentence stem “I am confident that I can start using an eHealth application and continue until I see my therapist.” The sentence stem will be followed by items representing technological and coping related barriers. Participants will respond on a 5-point scale ranging from not at all confident to very confident. Cronbach's alpha (.95) showed high internal consistency in a young adult sample. This scale will provide quantitative data on patient pre-self-efficacy.

**eHealth Intervention Self-Efficacy** (Yeager et al, 2018), 8-items that begin with the stem “I am confident I could continue to use an eHealth intervention over the next two weeks” followed by items measuring treatment self-efficacy related technology and depression coping self-efficacy.

Participants will respond on a 5-point scale ranging from not at all confident to very confident. This scale has high internal consistency with Cronbach's alpha of .94-.96. This scale will provide data on patient post-intervention self-efficacy.

**Acceptability of intervention:** Rate of agreement to participate and study enrollment factors.

**Engagement in intervention:** Percentage of prompts completed/participation days. Other outcomes will be extracted as themes from our analyses of semi-structured interviews.

Intervention: Patients will receive text prompts once a day on their own phones with a Qualtrics survey link (see

Appendix 2 and detailed description of intervention content in Aim 2). Participants will receive feedback on how their depression score compares to a nationally representative average extracted from MIDUS (Midlife in the United States: A national epidemiological study of health and well-being), data which we already have and used for publication ([name], [name], et al, 2018; [name], [name], under review).

Quantitative Analyses:

**Data processing.** Data will be checked for out of range values and missing data where appropriate through

plotting and descriptive analyses. Finally, data will be transformed as needed to create the variables of interest (e.g. age of depression onset as age of first episode visible in the EHR).

**Missing Data Strategies.** We will minimize the level of missing data (due to loss to follow-up, withdrawal, or missing assessments) to the extent possible. If missing data occur, I will work with [name] to assess the missing data mechanism for data missing due to loss to follow-up or withdrawal. I will compare baseline measures (e.g.,

demographics, clinical history, etc.) between subjects that have complete outcome data and those that do not

using logistic regression. Multiple imputation will be used for missing data in conjunction with a pattern of missingness. Missing data will be evaluated on an ongoing basis and recruitment may be continued beyond the original sample to achieve the desired power for the proposed analyses.

*Data Analysis. First, descriptive analyses will be performed on all baseline patient characteristics extracted for all patients approached for study enrollment, including those who agreed and did not agree to participate. To compare these two groups, we will use student t-tests (for continuous variables) and chi-square analysis (for categorical variables). This information will be used to derive acceptability of the proposed intervention. Next, descriptive analyses will be performed on the baseline questionnaires collected from the group of participants enrolled. This will give us additional data about patient characteristics that may further refine our phenotypes or improve study feasibility in the future. Engagement will be derived from percentage of prompts completed per days of participation in the intervention. Finally, we will calculate rates of treatment initiation (and corresponding 95% confidence interval) and compare to the initiation rate identified in our recent study on the Aim 1 cohort. To compare study treatment initiation to rates observed in Aim 3 to those in Aim 1 sample we will calculate the 95% confidence interval (CI) for the difference score between proportions (see Franklin, 2007). A significant difference will be denoted if the 95% CI does not include zero (Cumming & Finch, 2005). I will use negative binomial regression which accounts for overdispersion if treatment initiation is low (Coxe, West, & Aiken, 2009).*

Qualitative interviews and analysis: The interviews will be conducted using a semi-structured interview guide (see Appendix 3) and the same methods as Aim 2 interviews and analysis. These interviews will focus on the user's experiences using the self-monitoring intervention. Feedback will be sought about the functionality of the intervention, its perceived use, and ways to enhance it. We will specifically inquire about patients' perceptions about the three parts of the intervention: the symptom self-monitoring, practical support (i.e., appointment reminders), and emotional support (i.e., encouragement). Patients will also be asked to provide suggestions for emotionally supportive messages patients may want to see as they prepare to attend mental health sessions. Qualitative data will be analyzed in the same manner as presented in Aim 2.

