Treatment initiation	A primary or secondary stop code showing a visit in mental health (with a psychologist or psychiatrist) or primary care AND an ICD9 for depression diagnosis.

Sampling plan and data extraction and processing:

**Data source and cohort selection.** We will use data from the VA Corporate Data Warehouse (CDW), a centralized data repository which contains electronic medical records of all Veteran patients who receive care through the VHA. The patient cohort (N = 88,456) used for completion of Aim 1 includes 1) OEF/OIF Veteran patients with a PHQ9  $\geq$ , 2) who were not already in treatment for depression prior to this PHQ9 assessment, 3) were never diagnosed with bipolar, personality, psychotic, and pervasive developmental disorders to be consistent with the National Committee on Quality Assurance measure of quality of care, HEDIS (HEDIS, 2018), as well as substance dependence or patients who are in treatment for substance related disorders at the time of recruitment. The exclusion criteria are based on the fact that the presence of these disorders may result in divergent treatment practices compared to unipolar depression in the absence of these conditions. Our primary outcome, treatment initiation, is conceptualized as a combination of service encounters with specialty mental health (psychologists, psychiatrists) or primary care providers charted into the patients' VHA medical records (excluding assessments) that were associated with any depressive disorder diagnosis. Our data are already IRB exempt, R&D and DART approved, and have already been extracted.

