*Fortunately, the EHR is rich in terms of wealth of potential predictors to carry out the analyses. This work is a first step in the development of an automated system that can be implemented in the VHA EHR to more easily identify patients who may be in need but at risk for lack of engagement in mental health treatment.* A direct logistic regression will be performed to evaluate the battery of proposed and potential factors as possible predictors of lack of treatment engagement. The final model will be estimated using the validation sample (half of our overall available sample). Regression (beta) coefficients and odds ratios will be extracted for interpretation and evaluation of risk to not engage in treatment in our next step.

*Computation of health service utilization risk score.* Using coefficients extracted from final logistic regression testing the best fitting patient phenotype associated with lack of treatment engagement, we will compute a risk score for lack of treatment engagement. This score will be used to select high risk patients enrolled in our intervention development and evaluation studies (Aims 2 and 3). The logistic regression equation will be used to calculate the risk scores using the intercept and co-variated specific coefficients that relate to the probability of lack of treatment initiation. Therefore, the equation will be based on the logistic regression model which will be developed in the log odds scale.

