#### A4b. Aim 2.

Study/Design overview: This aim is phase 1 focusing on the formative development of the eHealth intervention using a human-centered design (see Appendix 2). *Guiding the development of this Aim (and Aim 3) will be Levesque’s Framework which proposes that patient’s ability to engage is at the core of successful health care consequences (i.e., outcomes). Therefore, the focus will be on providing patients the mechanism to initiate treatment. This will be done via active self-monitoring and specific labeling of depression symptoms, as well as via emotional and practical support. Based on this framework, the process by which behavior change about treatment is activated is by helping patients more clearly identify health care needs (i.e., via symptom monitoring) help rectify perception of needs (by providing feedback on symptoms, whether they are elevated and a provider should be contacted), helping with care seeking and reaching (i.e., sending provider contact information and sending reminders).*

Sample: This aim will be achieved by involving 10 stakeholders (patient n = 6 and provider n = 4). Patients will be selected based on risk scores generated in Aim 1 and the following inclusion/exclusion criteria. Patient and provider input will be used to revise intervention content.

Table 2. Patient inclusion/exclusion criteria for Aims 2 and 3.

Inclusion criteria:

- OEF/OIF Veteran: high prevalence of depression in this population and generalizability across adult ages
- PHQ9 $\geq 10$ ; DSM-5 criteria for major depressive disorder will be used to extract an MDD diagnosis.
- No gender or minorities will be excluded from this study; all ages will be included.

Exclusion criteria:

- Current/Past Bipolar disorder and Current Psychotic disorder: to avoid potential exacerbation from treatment for depression
- Alcohol Use disorder or Substance Use disorder: Depression treatments cannot reverse the adverse effects of substances on mood, and therefore impact on adherence and treatment characteristics may be confounded

- Other current severe or unstable, psychiatric and medical disorders that necessitates clinical management that can confound results (e.g., cancer [in chemotherapy], suicidality, recent hospitalization [medical/surgical] for which recovery overlaps with study onset and duration, open skull/brain injury, moderate to severe TBI)
- Moderate to severe cognitive impairment (SLUMS  $\leq 20$  and/or diagnosis in medical record)

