- Potentially temporary states/situations that may significantly impair mood/capability to engage in treatment: unstable environment that is not in one's control (e.g., homeless, temporary group home, extensive care taking duties).

Sampling plan: The target population is a clinical sample of Veterans with depression who meet the criteria in Table 2. Exclusion criteria are consistent with conventional depression studies. Veterans will be excluded if they have a medical disorder that would significantly increase their risk of depression secondary to a medical diagnosis or due to treatments for those medical diagnoses (e.g., cardiovascular disease; SUD) or those experiencing side effects with standard treatment or would require a significant adaptation of treatment (e.g., bipolar disorder). Veterans will also be excluded consistent with the standard of care for cognitive and/or behavioral treatment of depression at Tampa VA (e.g., actively suicidal patients that need intensive and immediate treatment). Patients will need to have a risk score associated with lack of treatment initiation as determined in Aim 1.

Recruitment: The Tampa VA is an ideal site because it has a large and diverse mental health population. In FY17 over 2000 patients had a first visit to primary and specialty mental health care, with over half showing a depression diagnosis in their charts. Veterans will be recruited using the following methods: 1) Depression treatment consults. Veterans referred for mental health treatment (psychotherapy or medication) through the mental health consult service will be informed about the proposed CDA clinical trial either by their provider or the study RA who will regularly monitor MH referrals on CPRS. 2) Advertisement. IRB-approved brochures will be placed throughout Tampa VA (e.g., primary care, pharmacy). Interested Veterans can contact study staff to learn more about participating. 3) Referrals from providers. Tampa VA providers in primary care - mental health service lines will be informed of the study and given research brochures. Providers can then give information to Veterans referred to specialty care for treatment.

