An eHealth intervention to increase depression treatment initiation and adherence among veterans referred for mental health services (CDA 18-189)

NCT05990075

November 30, 2022

*Analysis plan:*

*Data processing.* Data will be checked for out of range values and missing data where appropriate through plotting and descriptive analyses. Finally, data will be transformed as needed to create the variables of interest (e.g. age of depression onset as age of first episode visible in the EHR). *Missing Data Strategies.* We will minimize the level of missing data (due to loss to follow-up, withdrawal, or missing assessments) to the extent possible. If missing data occur, I will assess the missing data mechanism for data missing due to loss to follow-up or withdrawal. I will compare baseline measures (e.g., demographics, clinical history, etc.) between subjects that have complete outcome data and those that do not using logistic regression. Multiple imputation will be used for missing data in conjunction with a pattern of missingness. Missing data will be evaluated on an ongoing basis and recruitment may be continued beyond the original sample to achieve the desired power for the proposed analyses. *Data Analysis.* First, descriptive analyses will be performed on all baseline patient characteristics extracted for all patients approached for study enrollment, including those who agreed and did not agree to participate. To compare these two groups, we will use student t-tests (for continuous variables) and chi-square analysis (for categorical variables). This information will be used to derive acceptability of the proposed intervention. Next, descriptive analyses will be performed on the baseline questionnaires collected from the group of participants enrolled. This will give us additional data about patient characteristics that may further refine our phenotypes or improve study feasibility in the future. Feasibility will be derived from percentage of prompts completed per days of participation in the intervention. Finally, we will calculate rates of treatment initiation (and corresponding 95% confidence interval) and compare to the initiation rate identified in the literature. To compare study treatment initiation to rates we will calculate the 95% confidence interval (CI) for the difference score between proportions (see Franklin, 2007). A significant difference will be denoted if the 95% CI does not include zero (Cumming & Finch, 2005).

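### Aim 3 declares significance for initiation in 15 risk-selected Veterans against a reference not restricted by risk or referral (protocol) or not named (SAP)

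*Protocol*

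**What the plan says.** **Who is in Aim 3.** Protocol A4c plans 15 patients in one group, and "Participant recruitment and sampling will follow steps described in Aim 2". Under the A4b sampling plan, "Patients will need to have a risk score associated with lack of treatment initiation as determined in Aim 1". A4a (computation of the risk score) likewise says the score will pick high-risk patients for Aims 2 and 3. A2 and the opening of A4 describe the target population as already referred and waiting for a first visit. Brochure advertising is also a recruitment route (A4b, Recruitment), and referral is not a listed criterion in Table 2.

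**What they are compared with.** Protocol A4c, Data Analysis: "compare to the initiation rate identified in our recent study on the Aim 1 cohort". A4a defines that cohort: "The patient cohort (N = 88,456) used for completion of Aim 1 includes 1) OEF/OIF Veteran patients with a PHQ9" at or above the threshold, not already in depression treatment, with diagnostic exclusions. No risk-score or referral restriction is listed. The SAP has "compare to the initiation rate identified in the literature", with no source, population or figure.

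**The rule.** Both documents carry the same sentence: "A significant difference will be denoted if the 95% CI does not include zero".

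**Time.** The A4a analysis plan sets three initiation windows (3, 6 and 12 months) counted from the PHQ9 date. Neither A4c nor the SAP gives a window or a start date for Aim 3 initiation.

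**The concern.** The plan selects people because they are predicted to start treatment less often, then tests their rate against people who were not selected that way. Any risk score that works makes the two rates differ before the intervention does anything. Referral probably pushes in the opposite direction, since a referred patient is already one step into care. No subgrouping, standardisation or adjustment is planned to separate these effects from the intervention.

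The zero rule turns that difference into a declared finding. A pilot could therefore report a significant gain or loss in initiation that reflects who was enrolled, or which reference was picked. Results will be published and will inform the follow-up application (A5), and the proposed randomised trial tests initiation (A7), so a spurious signal could reach that design.

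**Working it through.** **What can be reproduced.** Neither document gives an Aim 1 initiation rate, a literature rate, a target difference or a power figure, so there is no planned figure to reproduce. The figures below illustrate how the rule behaves under stated assumptions.

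**Inputs**
- n = 15 (A4c); reference N = 88,456 (A4a).
- Reference rate: assumed. The values 18.5% and 27% are the ends of the A1 range for any mental health care use, which is not an initiation rate. Neither document names them as the reference. Values of 40% and 50% are added for range.
- AUC 0.8: the example benchmark for good fit in A4a, not an expected result. An AUC of 0.7 is the sensitivity case.
- Selection: everyone above a Youden cut-off on an equal-variance binormal score. This is assumed; A4a says only that an optimal ROC cut-off will be sought.
- CI type: the plan gives only a citation, so both Wald and Newcombe are shown.

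**Step 1. Counts that trigger the rule against 27%.**
- Wald: d ± 1.96·√[p₁(1−p₁)/15 + p₂(1−p₂)/88,456].
- Newcombe: the same difference d, with limits built from the Wilson limits of each proportion.
- A gain needs 8 or more of 15 with either method.
- A loss needs 0 of 15 (Newcombe) or at most 1 of 15 (Wald).
- Example, 1/15: d = 0.067 − 0.270 = −0.203. Wald gives −0.330 to −0.077, which excludes zero. Newcombe gives −0.258 to +0.028, which does not.

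**Step 2. Effect of risk selection alone.** Separation = √2·Φ⁻¹(0.8) = 1.190. The share of non-initiators above the cut-off is Φ(0.595) = 0.724, and of initiators Φ(−0.595) = 0.276. Being above the cut-off multiplies the odds of initiation by 0.276/0.724 = 0.381. From 27%: odds 0.27/0.73 = 0.370; 0.370 × 0.381 = 0.141; rate 0.141/1.141 = 12.4%.

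**Step 3. How often the rule fires with no intervention effect (reference 27%, AUC 0.8).**

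| Referral effect | Natural rate | False gain | False loss, Newcombe | False loss, Wald |
|---|---|---|---|---|
| None | 12.4% | under 0.1% | 13.8% | 43.1% |
| Exactly cancels selection (OR 1/0.381 = 2.6) | 27% | 2.7% | 0.9% | 5.8% |
| OR 4.7 | 40% | 21.3% | 0.1% | 0.5% |
| OR 7.1 | 50% | 50.0% | under 0.1% | 0.1% |

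First row: with the unrounded rate of 0.1235, P(X=0) = 0.8765¹⁵ = 0.138, and P(X≤1) = 0.138 + 15 × 0.1235 × 0.8765¹⁴ = 0.431. The odds ratios come from the target odds over 0.141, for example (0.40/0.60)/0.141 = 4.7.

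**Step 4. Sensitivity.**
- AUC 0.7, reference 27%, no referral effect: multiplier 0.551, natural rate 16.9%, false loss 6.2% (Newcombe) or 25.1% (Wald). The cancelling odds ratio is 1.8. Natural rates of 40% and 50% need odds ratios of 3.3 and 4.9.
- AUC 0.8, no referral effect, references of 18.5%, 40% and 50%: natural rates 8.0%, 20.3% and 27.6%. False loss is 0%, 38.9% and 37.2% (Newcombe) or 28.8%, 38.9% and 59.9% (Wald).

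**Step 5. Choice of reference.** With 7/15, the Newcombe interval is +6.3 to +51.4 points against 18.5% (significant) and −2.2 to +42.9 against 27% (not significant). Wald agrees on both verdicts. This count shows a reversal. Between these two references the verdict changes at only 3 of the 16 possible counts with Newcombe (0, 6, 7) and 2 with Wald (1, 7).

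**The case against.** **Aim 3 is formative.** Its stated purposes in A4c are usability, acceptability, engagement with the intervention and problems in running it. Initiation is analysed last, no go/no-go decision hangs on it, and A7 plans a controlled trial. The plan does not explicitly attribute a difference to the intervention. All of this stands and limits the consequence. It does not remove the significance rule, which is written into both documents.

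**The two references may be one.** A3a describes an initiation paper from the same data, which might be both the recent study and the literature. If so, the protocol and SAP differ only in wording. The documents do not settle this, so a firm contradiction cannot be claimed, only that the passages must be reconciled.

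**The biases may cancel.** They may, and the rule then behaves much closer to nominal. The documents give no basis for assuming it.

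**Stronger readings the documents do not support**
- That the windows are mismatched. Aim 3 states none, so comparability in time is unspecified, not shown to be wrong.
- That a false gain in 21% to 50% of pilots is to be expected. It needs referral odds ratios of 4.7 to 7.1 (3.3 to 4.9 at AUC 0.7), which nothing in the documents supports.
- That the whole-cohort reference is the main reason a real gain would be missed. A true rise from 12.4% to 27% is called a gain in 2.7% of pilots against 27%. Against a perfectly matched 12.4% it would be called a gain in only 38% (Newcombe, 5 or more of 15) or 20% (Wald, 6 or more). With n = 15 most such gains are missed even then.

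**Conclusion.** The concern holds in this form: both documents apply a significance rule to the initiation rate of 15 risk-selected, mostly referred Veterans. The reference is unrestricted by risk or referral in the protocol and unnamed in the SAP, and Aim 3 fixes no window. The rule can therefore declare a gain or loss unrelated to the intervention.

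The direction and size of the net bias are unknown. Under the assumed 27% reference with no intervention effect, the result runs from false loss in 14% to 43% of pilots (AUC 0.8, no referral effect) to 0.9% to 5.8% loss and 2.7% gain (exact cancellation). These figures rest on an assumed reference rate, AUC and cut-off and show only how the rule can behave. A reader might infer that the pilot is biased in one known direction, or that matching on risk would cure the problem. Neither follows, because the referral effect would remain.

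This should be fixed. The consequence is moderate, since the pilot is formative and a randomised trial is planned to test initiation. Nothing here is a criticism of 15 patients for usability work.

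**What to change.** In both the protocol (A4c, Data Analysis) and the SAP:

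1. Delete the rule that calls the initiation difference significant when the 95% CI excludes zero.
2. Report the Aim 3 initiation rate descriptively, with a Wilson or exact 95% CI.
3. Reconcile the two references: name one source, one of the three A4a windows, the same outcome definition as Aim 1, and a stated start date for counting.
4. Show the Aim 1 rate above the same risk cut-off beside the whole-cohort rate, both labelled as context.
5. State that the risk-matched rate does not correct for referral, consent, the single site or the Table 2 criteria. Add that, because referral probably raises initiation, this reference probably favours the intervention. In the cancellation case above it would show 27% − 12.4% = 14.6 points of apparent gain with no effect. No gain or loss should therefore be attributed to the intervention.

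Cost: a few sentences in each document. The risk-matched rate comes from data and scores already planned for Aim 1, with no new patients. The downside is that Aim 3 makes no significance claim about initiation, a claim this uncontrolled pilot could not support.
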